### **4.2 Sample size**

According to the mean and standard deviation of the two groups of neutralizing

antibody,  $1323 \pm 1093.9$  in the experimental group and  $164.8 \pm 123.4$  in the control group; using the standard deviation combined formula  $s = \sqrt{\frac{s_1^2(n_1-1)+s_2^2(n_2-1)}{n_1+n_2-2}}$ , the combined standard deviation was calculated as 778.4.

With reference to the above results, it was determined that the expected difference between the outcome indicators of the experimental and control groups in this study was 1158.2, and the standard deviation was 778.4. Taking the test level  $\alpha = 0.05$  and the degree of certainty  $1-\beta = 0.9$ , the minimum sample size for each group was calculated as 10 people according to the following formula, and setting the expected loss of follow-up rate at 20%, 13 people needed to be recruited in each group.

$$N = 2 \times \left( \frac{Z_{1-\frac{\alpha}{2}} + Z_{1-\beta}}{\delta} \right)^2 \times s^2$$

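### The 90% power stated for 10 evaluable people per group comes from a normal-quantile formula; on the same means and SDs, t-based tests on normal raw-scale data give about 88% (equal variance) or 84% (Welch)

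*Protocol*

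**What the plan says.** Protocol section 4.2 takes neutralizing antibody values of 1323 (SD 1093.9) for the experimental group and 164.8 (SD 123.4) for control. It pools the two SDs and reports that "the combined standard deviation was calculated as 778.4". It then states that "the expected difference between the outcome indicators of the experimental and control groups in this study was 1158.2". With alpha 0.05, entered through the two-sided 1 − α/2 quantile, and 1 − β = 0.9, it applies N = 2 × ((Z₁₋α/₂ + Z₁₋β)/δ)² × s² and concludes that "the minimum sample size for each group was calculated as 10 people". After an allowance of 20% for loss to follow-up, "13 people needed to be recruited in each group".

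The section makes no small-sample or unequal-variance adjustment and names no test for the comparison.

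**The concern.** The formula is a large-sample approximation that treats the SD as a known constant. It is used here to arrive at 10 people per group, where the SD is estimated from very few observations and a comparison of means needs a t critical value. The two SDs also differ almost nine-fold. An unequal-variance test would then rest on roughly the degrees of freedom of the more variable group alone.

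Section 4.2 is the protocol's only justification of the trial's size. If the 90% is not what a test on these inputs delivers at the planned loss, readers are given too favourable a figure for the chance of detecting the assumed difference.

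**Working it through.** **Inputs, all from Protocol section 4.2:** means 1323 and 164.8; SDs 1093.9 and 123.4; two-sided alpha 0.05; target power 0.90; equal groups; loss 20%.

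**1. The protocol's own figures reproduce.**
- Difference: 1323 − 164.8 = 1158.2.
- Pooled SD with equal groups: √((1093.9² + 123.4²)/2) = 778.4.
- N = 2 × ((1.960 + 1.282) × 778.4/1158.2)² = 9.49, rounded up to 10.
- Recruitment: 10/0.8 = 12.5, rounded up to 13.
- At n = 10 the same normal approximation credits the design with 91.4% power.

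**2. Pooling is not the cause.** At n = 10 the standard error of the difference is √(1093.9²/10 + 123.4²/10) = 348.1 from the separate SDs, and 778.4 × √(2/10) = 348.1 from the pooled SD. With equal groups the two are the same.

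**3. Replace the normal quantile by t at n = 10.** The non-centrality is 1158.2/348.1 = 3.33 in every case. Only the critical value and the degrees of freedom change. Welch's degrees of freedom are (n − 1)(s₁² + s₂²)²/(s₁⁴ + s₂⁴) = 9.2.

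| Test, n = 10 per group | df | Critical value | Power |
|---|---|---|---|
| Normal approximation (protocol) | – | 1.96 | 91.4% |
| Equal-variance t | 18 | 2.10 | 88.2% |
| Welch | 9.2 | 2.25 | 84.3% |

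Simulating normal data with the two stated means and SDs (200,000 runs) gives 87.5% for the equal-variance test and 84.2% for Welch.

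**4. Which test holds alpha.** With equal means, the two stated SDs and n = 10, simulation shows the equal-variance test rejecting about 6.4% of the time and Welch about 5.1%. On these inputs Welch's test is the one that keeps the stated 0.05.

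**5. Size needed for 90% (non-central t).**

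| Evaluable per group | Equal-variance t | Welch |
|---|---|---|
| 10 | 88.2% | 84.3% |
| 11 | 91.3% | 88.3% |
| 12 | 93.6% | 91.3% |
| 13 | 95.3% | 93.6% |

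So 90% needs 11 (equal-variance) or 12 (Welch) evaluable. At 20% loss that is 11/0.8 = 13.75, so 14 recruited, or 12/0.8 = 15 recruited.

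**6. If the titres are skewed (an assumption).** The SDs are 83% and 75% of their means. A normal model with these values puts about 11% of experimental and 9% of control titres below zero, so the raw-scale normal model fits poorly. Matching a log-normal to each mean and SD gives an SD of ln titre of √ln(1 + (1093.9/1323)²) = 0.72 and √ln(1 + (123.4/164.8)²) = 0.67, about 0.70 combined. The implied geometric mean ratio is 7.7. Simulated power at n = 10 is then about 98.5% (equal-variance) and 97.4% (Welch) on raw titres, and above 99.9% on log titres. For a t test on log titres at n = 10, 90% power needs a non-centrality of 3.43. The detectable ratio is therefore exp(3.43 × 0.695 × √(2/10)) ≈ 2.9.

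**The case against.** The strongest reply is that the protocol states its inputs and its formula, and they agree. A reader who sees t-based power below 90% might infer a calculation error; there is none. A reader might also blame the pooled SD, but with equal groups it leaves the standard error unchanged. The loss comes from using z in place of t and from Welch's lower degrees of freedom.

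It is also fair to say that the ordinary t-test gap is under 2 points by the non-central t and costs one person per group. The larger Welch gap depends on a test the protocol does not name, and the choice of test and scale may properly sit in an analysis plan that is not at hand. That choice is not criticised here. Welch serves as the benchmark because, with the protocol's own SDs, the equal-variance test does not hold the stated alpha.

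The most tempting stronger reading is that the trial is underpowered. The document does not support that. The shortfall needs normal raw-scale titres, a model the protocol's own figures fit poorly, and it needs the full 20% loss. Under the log-normal assumption, power for the assumed effect is well above 90%. With no loss it is above 90% even under the normal model.

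What remains is that the 90% is too high under the normal-means calculation the section uses.

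**Conclusion.** The point holds in a limited form. Under a raw-scale normal model with the protocol's means and SDs, two-sided alpha 0.05 and 10 evaluable per group, power is about 88% (equal-variance t) or 84% (Welch), not 90%. The Welch gap is nearly 6 points, or two evaluable people per group. This is a choice of approximation that is slightly optimistic at this size. It calls for a corrected statement of power and gives no ground for saying that the trial is too small for the effect it assumes.

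**What to change.** Keep 13 recruited per group and restate the power in section 4.2 from a t-based calculation, naming the scale and test it assumes. Two wordings would do:

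- **Raw scale kept:** about 84% power with Welch's test at 10 evaluable per group, for a difference of 1158.2 with SDs 1093.9 and 123.4.
- **Log scale, if titres are to be analysed that way:** 90% power at 10 evaluable per group for a geometric mean ratio of about 2.9, with an SD of ln titre of about 0.70, noting that this SD was derived by moment matching from the quoted means and SDs.

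The cost is one reworded paragraph and no extra participants. If the raw scale is kept, the stated power becomes less favourable.

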### 4.3 Randomizing

Using the random number method, the study subjects were randomized into four groups, performed on R version 4.1.3, and after 3 days of a low-volume diet of a certain nutrient, nutritional supplement intervention was performed 3 days before the first dose of vaccine to the second dose of vaccination, in which the first group will receive nutritional supplements of 500mg/day from days 3 of the study; The second group will receive nutritional supplements 500mg/day, starting on days 6 of the study; The third group will receive a placebo and days 3 of the study.

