### Grouping concealment

After randomly grouping the study subjects, the groupings will be replaced with numbers 1, 2, and 3 to mask the specific grouping information.

Using the envelope method, the number of each study subject's grouping was placed in an envelope according to the grouping, and the name and ID were written on the outside of the envelope and distributed to each study subject.

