### Masking:

The three-blind design was adopted, and the study implementers, research subjects, data monitoring and statistical analysts were blinded.

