#### **Supplements used in interventions:**

Placebo group: six ×500 mg sunflower oil capsules each day.

Day 3 ARA group: 512.4mg/day ARA via 6 × 500mg ARA capsules.

Day 6 ARA group: 512.4mg/day ARA via 6 × 500mg ARA capsules.

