### **Biological sample collection (6 times in total):**

Test Day 3: venous fasting blood collection of 30 ml and feces of 10 g;

Trial Day 6 (vaccination Day 0): 5 ml of blood collected intravenously; 10 g of feces;

Trial Day 13 (vaccination Day 7): 5 ml of blood collected intravenously on an empty stomach; 10 g of feces;

Trial Day 16 (vaccination Day 10): 5 ml of blood collected intravenously; 10 g of feces;

Trial Day 19 (vaccination Day 13): 30 ml of blood collected intravenously; 10 g of feces;

Trial Day 26 (vaccination Day 20): 5 ml of blood collected intravenously; 10 g of feces.

Preservation of serum, plasma and whole blood: frozen at -80°C after sampling.

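### The Day 6 ARA arm starts capsules three days after the other arms with no placebo lead-in listed, so the start day can reveal ARA despite the stated triple blind

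*Protocol*

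**What the plan says.** Section 4.3 (Randomizing) sets a general window for the supplement: "nutritional supplement intervention was performed 3 days before the first dose of vaccine to the second dose of vaccination". It then gives start days by group. The first group, on the supplement, starts on Day 3. The entries for the second group, also on the supplement, and for the placebo group run: "starting on days 6 of the study; The third group will receive a placebo and days 3 of the study". The placebo wording is garbled, but Day 3 is the only day it names. The same sentence says that "the study subjects were randomized into four groups", although only three groups are described.

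The list of supplements gives six sunflower-oil capsules a day to the placebo group only. For the late-start arm it has a single entry: "Day 6 ARA group: 512.4mg/day ARA via 6 × 500mg ARA capsules". No dummy capsules appear there for Days 3 to 5.

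On concealment, "the groupings will be replaced with numbers 1, 2, and 3 to mask the specific grouping information". Each participant's number goes into an envelope; "the name and ID were written on the outside of the envelope and distributed to each study subject". On masking, "The three-blind design was adopted, and the study implementers, research subjects, data monitoring and statistical analysts were blinded".

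**The concern.** Capsules of identical appearance can hide what is taken, but not the day on which taking starts. If one arm starts three days after the others and that arm is always ARA, the start day gives away the treatment. The people who see the start day are the participant and the staff who dispense, and both are among those the protocol calls blinded.

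The coding scheme adds to this. Each arm has one shared number, so a single known Day 6 starter identifies the number of the whole arm to anyone who sees both the number and the start day.

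The outcomes most open to influence are the participant-reported safety items in section 4.4 (adverse reactions such as gastrointestinal discomfort, and GAD-7), which serve the stated safety objective. Adherence and withdrawal are also open to it, because section 4.1 (Drop out) makes both not taking the supplement as prescribed and voluntary withdrawal grounds for dropping out. The two primary indicators, antibody titre and neutralizing antibody, are laboratory measures and less exposed.

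**Working it through.** **Group size (section 4.2).** This is needed only to count the participants affected. Pooled SD with equal groups: √[(1093.9² + 123.4²)/2] = 778.4. Difference: 1323 − 164.8 = 1158.2. With two-sided α = 0.05 and power 0.9, N = 2 × [(1.960 + 1.282)/1158.2]² × 778.4² = 9.49, rounded up to 10. Allowing for 20% loss, 10/0.8 = 12.5, rounded up to 13. The protocol's 10 and 13 per group are reproduced. The blinding point does not depend on them.

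**Arms by start day and listed product (section 4.3).**

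| Arm | Start day | Product listed | Listed for Days 3–5 |
|---|---|---|---|
| Day 3 ARA | Day 3 | ARA capsules, six a day | ARA |
| Day 6 ARA | Day 6 | ARA capsules, six a day | nothing |
| Placebo | Day 3 (garbled wording) | sunflower-oil capsules, six a day | placebo |

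**What the start day reveals, with 13 per arm.**
- P(ARA | Day 6 start) = 13/13 = 1.
- P(ARA | Day 3 start) = 13/(13 + 13) = 0.5.

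**The general window.** The sampling schedule has "Trial Day 6 (vaccination Day 0" as the day of the first dose. Three days before it is 6 − 3 = Day 3. The window stated for the intervention as a whole therefore opens on Day 3, which does not fit a group that starts on Day 6. A placebo lead-in would make the two agree, but none is written.

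**The unexplained fourth group.** If it took placebo from Day 6, P(ARA | Day 6 start) would be 13/(13 + 13) = 0.5 and the start day would no longer reveal ARA. The protocol does not describe such a group. The concealment codes stop at 3, and the supplement list has three entries.

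**Share affected.** 13/39 = 33.3% with three groups; 13/52 = 25.0% with four.

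**Who could be unblinded.**
- Dispensing staff who know the design: yes, from the start day alone.
- Participants: only those who know that a Day 6 start always goes with ARA.
- Data monitors and analysts: only if they see start dates alongside codes, which the protocol does not say.

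**The case against.** The strongest reply is that this argues from silence. The supplement list gives product and daily amount, not a day-by-day schedule, and nowhere says that the Day 6 arm takes nothing on Days 3 to 5. The general window opens on Day 3 and the protocol claims full blinding, so a lead-in may be intended and simply unwritten. What stands is that the intention cannot be known from the text. But the explicit Day 6 start and the absence of any dummy capsules leave the stated blind unsupported, and the text needs changing on either reading.

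The key sentence is also damaged: the placebo start is garbled, and it counts four groups while describing three. This is a real limit, and the probability of 1 holds only for the three described arms. Three numeric codes and three product entries support that reading.

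A participant must know the arm structure to infer anything, and consent pages are not available, so what participants are told is unknown. That stands as a condition for participants, but it does not protect the blinding of staff who dispense to the schedule.

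The envelope argument needs someone to see both code and start day, and the protocol does not say that participants open the envelope. The shared code therefore aggravates the problem but is not its basis.

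Finally, the consequence is limited. The primary indicators are laboratory measures, GAD-7 is listed on Day 13 only, and no size of bias can be calculated from the document. This stands. The percentages above count participants in the affected arm; they do not measure bias.

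**Conclusion.** The concern holds. Followed as written, the schedule does not deliver the stated triple blind for the Day 6 ARA arm. With the three described arms, a Day 6 start identifies ARA with certainty to dispensing staff who know the design and to participants who know the arm structure. One of the two ARA-versus-placebo comparisons is affected. Start timing does not break the blind between Day 3 ARA and placebo.

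This rests on three assumptions: that placebo starts on Day 3, the only day the protocol names for it; that no undescribed group takes placebo from Day 6; and that the Day 6 arm takes no dummy capsules before Day 6. It should be fixed, but it does not in itself undermine the laboratory primary results.

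**What to change.** Give every arm six identical-looking capsules a day from Day 3. The Day 6 arm would take matching placebo on Days 3 to 5, with its ARA schedule left as it is. Replace the shared 1/2/3 codes with a unique kit number for each participant, and do not hand the arm code to participants.

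Reconcile the Randomizing, Grouping concealment, Masking and Supplements paragraphs of section 4.3 on three matters: the number of groups, the common intervention window, and what the Day 6 arm takes on Days 3 to 5.

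The cost is small: 6 capsules × 3 days = 18 placebo capsules per participant in one arm, and 18 × 13 = 234 in total, plus relabelled kits and a wording change. No extra visits or participants are needed.

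If the lead-in is not adopted, or allocation has already been carried out, a change of text is enough. State that participants and dispensing staff are not blinded for the Day 6 arm, and limit the triple-blind claim to Day 3 ARA versus placebo.

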### Grouping concealment

After randomly grouping the study subjects, the groupings will be replaced with numbers 1, 2, and 3 to mask the specific grouping information.

Using the envelope method, the number of each study subject's grouping was placed in an envelope according to the grouping, and the name and ID were written on the outside of the envelope and distributed to each study subject.

### Masking:

The three-blind design was adopted, and the study implementers, research subjects, data monitoring and statistical analysts were blinded.

#### **Supplements used in interventions:**

Placebo group: six ×500 mg sunflower oil capsules each day.

Day 3 ARA group: 512.4mg/day ARA via 6 × 500mg ARA capsules.

Day 6 ARA group: 512.4mg/day ARA via 6 × 500mg ARA capsules.

#### **4.4 Study content**

##### **Baseline Investigation**

- 1) Baseline data collection: age, gender, education level, monthly income, etc;
- 2) Collection of dietary intakes: 3-day, 24-hour dietary review method;
- 3) Lifestyle information: physical activity, sleep, anxiety, depression;

##### **Follow-up indicators:**

###### **1) Primary indicators:**

- ① Rabies virus antibody titers: to examine the specific antibody after intervention.

Will be tested on day 6, 13, 16, 19 and 26.

- ② Neutralizing antibody: to test the ability of binding to rabies virus

Will be tested on day 6, 13, 16, 19 and 26.

###### **2) Secondary indicators**

- ① Serum blood fatty acid profiles: to reflect the change of fatty acid profiles after intervention. Will be tested on day 6, 13, 16 and 19.

- ② Cytokines: to test the potential blood cytokines changes triggered by ARA supplementation. Will be tested on day 6, 13, 16, 19 and 26

- ③ Feces microbiota: the microbiota in feces samples will be examined with metagenome to explore the potential gut-immune response caused by intervention. Will be tested on Day 3, 6, 13, 16, 19 and 26 of the study.

- ④ Blood metabolites: To examine the metabolites changes in blood after intervention.

Will be tested on Day 6, 13 and 16 .

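### Serum fatty acids, cytokines and blood metabolites have no scheduled pre-supplement value common to all arms, although fasting blood is already drawn on Day 3

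*Protocol*

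**What the plan says.** **Start of supplementation (Protocol, 4.3 Randomizing).** The section describes a short diet run-in followed by supplementation: "after 3 days of a low-volume diet of a certain nutrient, nutritional supplement intervention was performed 3 days before the first dose". For the arms it says that "the first group will receive nutritional supplements of 500mg/day from days 3 of the study" and that "The second group will receive nutritional supplements 500mg/day, starting on days 6 of the study". The sentence on the third arm is garbled but appears to start placebo on Day 3. The section speaks of four groups but describes three.

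**Assay days (4.4, Secondary indicators).** Serum fatty acids are measured "to reflect the change of fatty acid profiles after intervention. Will be tested on day 6, 13, 16 and 19". Cytokines are included "to test the potential blood cytokines changes triggered by ARA supplementation", on Days 6, 13, 16, 19 and 26. Blood metabolites are also meant to show change after the intervention: "Will be tested on Day 6, 13 and 16". Faecal microbiota differs: "Will be tested on Day 3, 6, 13, 16, 19 and 26 of the study".

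**Blood drawn (4.4, Biological sample collection).** The first collection is "Test Day 3: venous fasting blood collection of 30 ml and feces of 10 g". Day 6 is vaccination Day 0. Fasting is stated only for the Day 3 and Day 13 draws. Serum, plasma and whole blood are to be frozen at -80°C. Under Safety indicators, the only Day 3 blood tests listed are glucose and lipids, and the blood count.

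**The concern.** Three mechanism panels are described as change after the intervention, yet each is first measured when one ARA arm, and apparently the placebo arm, has already had three days of capsules. Day 3 appears to be the only blood draw at which all arms share the same history (diet run-in, no capsules), provided the blood is taken before the first capsule. The protocol does not state that order.

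The Day 3 or Day 6 start is the only stated difference between the two ARA arms. A change measured from Day 6 would mean different things in them: change since before ARA in the later-starting arm (again if blood comes first), but change after three days of ARA in the earlier-starting arm.

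This is a matter for the protocol rather than the SAP. An SAP can choose a covariate, but it cannot analyse a value that was never assayed.

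**Working it through.** **1. The plan's own sample size (section 4.2).** This gives the arm sizes used below.

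- Pooled SD with equal groups: √[(1093.9² + 123.4²)/2] = 778.41; the plan states 778.4.
- Difference: 1323 − 164.8 = 1158.2.
- N = 2 × [(1.960 + 1.282)/1158.2]² × 778.4² = 9.49, rounded up to 10.
- Recruitment with 20% loss: 10/0.8 = 12.5, rounded up to 13.

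Both stated figures reproduce. The concern does not depend on them beyond the range of 10 to 13 per arm.

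**2. State of each arm at the first assay, Day 6.**

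| Arm | Capsules start | Exposure by Day 6 |
|---|---|---|
| Day 3 ARA | Day 3 | three days of ARA |
| Day 6 ARA | Day 6 | none, if blood precedes the capsule |
| Placebo | Day 3 (apparently) | three days of placebo |

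**3. Assay days against draws.**

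| Panel | Assay days | Day 3 listed? | Listed days with stated fasting |
|---|---|---|---|
| Fatty acids | 6, 13, 16, 19 | no | 1 of 4 (Day 13) |
| Cytokines | 6, 13, 16, 19, 26 | no | 1 of 5 (Day 13) |
| Metabolites | 6, 13, 16 | no | 1 of 3 (Day 13) |
| Faecal microbiota | 3, 6, 13, 16, 19, 26 | yes | not applicable |

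None of the three blood panels has a scheduled value before supplementation in all arms.

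**4. If Day 6 were used as the baseline.** The protocol does not say that it would be. Suppose a share f of the Day 13 effect is already present on Day 6. The change from Day 6 in the Day 3 ARA arm then keeps 1 − f of that effect: 90%, 75% or 50% for f of 10%, 25% or 50% (assumed values).

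**5. Chance imbalance that cannot be seen.** The difference between two arms' true baselines has an SD of √(2/n) outcome SDs: 0.447 at 10 per arm and 0.392 at 13. It exceeds 0.5 SD in about 26% and 20% of trials respectively.

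**6. Precision a Day 3 covariate could add.** The calculation is for one normally distributed analyte, two arms, two-sided 5% and 80% power, using the noncentral t. Unadjusted, the degrees of freedom are 2n − 2. With the covariate, the SD is multiplied by √[(1 − r²)(1 + 1/(2n − 4))] and the degrees of freedom are 2n − 3. The protocol gives no baseline-to-outcome correlation r, so r is assumed.

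For n = 10 and r = 0.5 the multiplier is √(0.75 × 1.0625) = 0.893.

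| Per arm | No covariate | r = 0.3 | r = 0.5 | r = 0.7 | Break-even r |
|---|---|---|---|---|---|
| 10: detectable difference (SD) | 1.325 | 1.307 | 1.187 | 0.979 | 0.256 |
| 10: equivalent unadjusted n | 10 | 10.2 | 12.2 | 17.4 | |
| 13: detectable difference (SD) | 1.145 | 1.119 | 1.016 | 0.838 | 0.217 |
| 13: equivalent unadjusted n | 13 | 13.6 | 16.2 | 23.4 | |

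At the plan's own 90% power the unadjusted figure at 10 per arm is 1.53 SD. Applying the same ratios (1.187/1.325 = 0.896 and 0.979/1.325 = 0.739) gives about 1.37 and 1.13 SD, so the choice of power hardly alters the relative gain.

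**7. Assay load.** Three arms of 13 make 39 participants, so 39 × 3 panels = 117 extra assays. If there were four arms of 13, it would be 52 × 3 = 156. The present lists hold 4 + 5 + 3 = 12 rounds, or 12 × 39 = 468 assays. Three more rounds make 585, an increase of 25%, and of one third for metabolites.

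**The case against.** **The loss is small.** The outcomes are secondary and serve the exploratory objective. Randomised comparisons of later levels are valid without a baseline, and between-arm contrasts can answer whether ARA changed these markers. The protocol never commits to within-person change from before supplementation. All of this stands. It is why no bias is claimed, and why the primary antibody outcomes are left out of the point: Day 6 is their pre-vaccination value.

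**Day 6 is a useful time point.** It precedes vaccination in every arm, and for Day 3 ARA against placebo it is a randomised measure of three days' supplementation. That is true, but it is still not a common pre-supplement value.

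**The material is probably already kept.** The freezing statement makes no exception for Day 3, and 30 ml is generous for the tests listed. This is fair: the value may still be recoverable later. However, nothing assigns Day 3 blood to these panels or reserves an aliquot for them.

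**The benefit is assumed, and the cost is not nil.** The correlation is unknown. It may differ by panel, may be lower where a non-fasting draw is compared with a fasting one, and may be weakened by vaccination. The panels have many analytes, so a single-analyte calculation is only illustrative. The protocol gives no assay prices, and 25% more assays is a real addition. These limits stand and bear on the size of the gain. They do not change the fact that Day 3 is missing from the three lists.

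**Choice of covariate usually belongs in the SAP.** Agreed. The protocol's part is to ensure that the measurement exists.

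**Conclusion.** The point holds as a worthwhile improvement; it does not threaten the primary result. Followed as written, the schedule gives no common pre-supplement value for any of the three blood panels, while faecal microbiota does have a Day 3 measurement.

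The schedule gives up three things: within-person change from before supplementation, a view of chance imbalance, and a possible gain in precision. For correlations of 0.5 to 0.7, that gain is equivalent to roughly 2 to 7 more people per arm at 10 per arm (12.2 and 17.4 against 10), and 3 to 10 more at 13 per arm (16.2 and 23.4 against 13). It is negligible at 0.3 and absent below about 0.26 (10 per arm) or 0.22 (13 per arm).

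The omission is certain from the text. Its remedy rests on Day 3 blood being taken before the first capsule and on enough of that sample remaining. The size of the gain rests on the assumed correlations. Day 3 also follows the diet run-in, so it would be a pre-supplement value, not one on habitual diet.

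**What to change.** - In Secondary indicators, add Day 3 to the assay days for serum fatty acids, cytokines and blood metabolites.
- In Biological sample collection, reserve a -80°C aliquot of the Day 3 fasting sample for these panels, and state that this blood is taken before the first capsule.
- State the fasting status of the Day 6, 16, 19 and 26 draws. Unless they are fasting, treat Day 13 as the like-for-like within-person comparison with Day 3 for fatty acids and metabolites, and read change on the other days with caution.
- Name the Day 3 value as the baseline covariate for these panels in all arms, here or in the SAP.
- Reconcile the number of groups and the placebo start day in section 4.3, since both bear on this schedule.

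The cost is 39 extra assays per panel, 117 in all for three arms of 13 (156 if four arms were intended), plus wording changes in two places for the sampling schedule. No visit or blood draw is added. If the assay budget is tight, storing the aliquots now keeps the option open.
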